1.3 Treatment

Until recently, a major limiting factor in expansion of treatment for HCV has been standard of care therapy with pegylated interferon, ribavirin, and more recently for genotype 1 disease, boceprevir and telaprevir. These medications have significant side effect profiles, response-based dosing regimens of over 6 months, and decreased efficacy in key groups including: those with genotype 1 disease, HIV coinfection, and cirrhosis. However, there has been dramatic improvement using all oral DAA regimens with sustained virologic response (SVR) rates over 90%, short-duration therapies and well-tolerated, simple regimens including among those with HIV coinfection. However, most data on the use of DAAs is from clinical trials, which often enroll a patient population not representative of the HCV epidemic. Therefore, few studies have been published addressing the efficacy of interferon-free, DAA-based HCV treatment among PWID. However, a study of patients on opioid substitution therapy who were treated with DAAs demonstrated equivalent efficacy and adherence, even amongst those with persistently positive urine drug screens(28), indicating that effective treatment of PWID with ongoing drug use may be feasible.

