2.2 Secondary Objective

1. Evaluate uptake of PrEP
2. Evaluate adherence to PrEP
3. Evaluate uptake of buprenorphine when clinically indicated (HIPS site only)
4. Evaluate retention in buprenorphine programs (HIPS site only)
5. Assess change in risk behaviors at baseline, during, and after HCV treatment

6. Evaluate the impact of active IDU vs non-injecting opioid misuse on efficacy of DAAs for the treatment of HCV
7. Evaluate the impact of OST on HCV treatment outcomes

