13.1 Description of the Analyses

The primary outcome is achievement of SVR12 in phase 1 (first 100 enrolled participants). The primary analysis of efficacy for phase 1 is intention-to-treat for the proportion of patients who achieve SVR along with exact two-sided 95% confidence intervals, overall and by sub-categories. All patients who receive at least one dose of direct acting antiviral are included in the intention-to-treat analysis and patients without follow-up data are considered to have treatment failure. Chi-squared or Fisher's exact test will be used to assess the association of SVR12 with baseline characteristics such as HIV-status, as well as on treatment factors such as medication adherence and OST status. Percentage and standard error will be calculated for each of the secondary outcome of PrEP and buprenorphine including uptake, adherence, and retention. In phase 2, participants without recent IDU (opioid misuse within 1 year but not within 3 months) will be compared to patients with recent IDU, and the impact of collocated OST vs non-collocated OST will be assessed.

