13.2 Sample Size Justification

Based on the available DAA drugs, we expect to be able to treat up to 200 patients for HCV, with primary efficacy analysis after the first 100 enrolled participants (phase 1). The SVR of the general US population for HCV-infected and non-injection drug users is estimated at >90%. We target in our population of injection-drug users no greater than a $\pm 10\%$ SVR difference from the standard 90% SVR. For the primary objective, we will have 85% power to reject the null hypothesis if the actual proportion of patients with SVR is 80% or higher at a 2-sided, $\alpha=0.05$ significance level.

14 Ethics/Protection of Human Subjects

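### Section 13.1 plans only significance tests for the SVR12 associations, and no measure for the phase 2 contrasts; each needs the risk difference with a 95% confidence interval

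*Combined protocol and SAP*

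**What the plan says.** The primary analysis in section 13.1 is the proportion with SVR12, with an exact two-sided 95% interval, overall and by sub-categories. For associations, a chi-squared or Fisher's exact "test will be used to assess the association of SVR12 with baseline characteristics such as HIV-status", and the same sentence adds on-treatment factors, naming adherence and OST status. No effect measure accompanies these tests.

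The last sentence of 13.1 turns to phase 2. Participants without recent injecting are to be compared with those with recent injecting, and collocated OST is to be assessed against non-collocated OST. No test, estimate or interval is named for either.

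Section 2.2 words the matching objectives as questions of size. Objective 7 is "Evaluate the impact of OST on HCV treatment outcomes", and objective 6 asks the same of active IDU against non-injecting opioid misuse. Collocation of OST is exploratory objective 6 in section 2.3.

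The only power statement, in section 13.2, concerns the one-sample primary objective: "we will have 85% power to reject the null hypothesis if the actual proportion of patients with SVR is 80% or higher". No power is claimed for any association.

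**The concern.** A p-value does not measure impact. It reports whether the data are surprising under no difference, and in small groups with high cure rates it will often be unremarkable even when the difference is substantial. The planned intervals by sub-category show how imprecise each proportion is. A reader cannot take from two separate intervals how large a difference between the groups remains plausible.

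At stake is whether objectives 6 and 7 get an interpretable answer. With the planned output, a report could carry several non-significant results and no statement of which differences in cure the data leave open. The primary SVR12 estimate is not affected.

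**Working it through.** **Inputs.**
- Two-sided alpha of 0.05: stated in 13.2 for the primary objective only ("at a 2-sided, $\alpha=0.05$ significance level"); assumed here for the association tests, for which no alpha is given.
- N = 100 per phase and 200 in all: Protocol Summary and 13.2.
- True SVR12 of 90% v 80%: an illustration. The figures come from 13.2, where they describe a one-sample target.
- Group splits: not in the documents, so a range is assumed.
- Missing outcomes count as failures (13.1), so N is not reduced for dropout.

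**1. The plan's own figure.** One-sample normal approximation, null 90%, true 80%, n = 100:

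z = (0.10 − 1.96·√(0.9·0.1/100)) / √(0.8·0.2/100) = (0.10 − 0.0588)/0.04 = 1.03, so power = 0.85. The stated 85% is reproduced, but it says nothing about between-group comparisons.

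**2. Two-group power, 50/50, approximate.**
- Standard error under no difference: √(2·0.85·0.15/50) = 0.0714.
- Standard error under 90% v 80%: √(0.09/50 + 0.16/50) = 0.0707.
- z = (0.10 − 1.96·0.0714)/0.0707 = −0.57, so power is about 29% and the miss rate about 71%.

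**3. Exact miss rates.** All pairs of binomial outcomes were enumerated and the probabilities of the non-significant tables summed, for 90% v 80%:

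| Split | Group at 80% | Chi-squared | Fisher |
|---|---|---|---|
| 50/50 | either | 70% | 81% |
| 30/70 | smaller | 70% | 78% |
| 30/70 | larger | 80% | 84% |
| 20/80 | smaller | 74% | 78% |
| 20/80 | larger | 86% | 90% |
| 100/100 (both phases pooled) | either | 48% | 56% |

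At 50/50 the corresponding power is 30.3% (chi-squared) and 19.5% (Fisher). For 80% power, n per group = (1.96·√(2·0.85·0.15) + 0.842·√(0.09 + 0.16))²/0.10² = 199, about twice what even a pooled, evenly split study would have.

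The result also depends on the assumed rates. At 50/50, 95% v 85% is missed 61% (chi-squared) or 76% (Fisher) of the time, and 80% v 70% is missed 79% or 84%.

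**4. What an interval would show.** Half-width = 1.96·√(p1(1−p1)/n1 + p2(1−p2)/n2):
- 50/50: ±11.8 points (90% in both groups) to ±13.9 (90% v 80%).
- 20/80, 90% in both groups: ±14.7 points.
- 100/100: ±8.3 points (90% in both groups) to ±9.8 (90% v 80%).

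**5. Example.** Suppose 45/50 v 40/50. Fisher's test gives p = 0.26. The exact intervals that 13.1 would report are 78-97% and 66-90%. Newcombe's method uses the Wilson limits, 78.6-95.7% and 67.0-88.8%:
- lower: 0.10 − √((0.900−0.786)² + (0.888−0.800)²) = −0.04
- upper: 0.10 + √((0.957−0.900)² + (0.800−0.670)²) = +0.24

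The difference is 10 points, with a 95% interval of about −4 to +24. None of the planned outputs shows that interval.

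**The case against.** The strongest reply is that this is an observational pilot that claims no power for these comparisons. HIV status is not itself an objective, and HCV adherence is only exploratory. Intervals by sub-category are planned, so small-group imprecision would be visible, and anyone with the counts can calculate an interval for the difference. The miss rates rest on assumed splits, and the association sentence is not expressly limited to phase 1. Pooling would bring the miss rate down to about half. Near the 50/50 split, chi-squared might well be chosen over Fisher, which favours the lower end of the range. For the phase 2 contrasts no test is named, so a criticism of chi-squared and Fisher does not reach them.

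Much of this stands. The numbers must carry their conditions, and the phase 2 gap is a missing method, not a wrong one. It does not remove the point: objectives 6 and 7 ask for impact, and the plan should supply the measure instead of leaving it to the reader.

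Three stronger readings are tempting and not supported.
- A reader might infer that the trial will report non-significance as no impact. The documents contain no such rule. They give no rule at all for reading a non-significant result.
- Section 1.3 says that a study of patients on OST "demonstrated equivalent efficacy and adherence, even amongst those with persistently positive urine drug screens". A reader might take this as the answer the trial expects. It describes a cited outside study. Section 1.3 concludes only that treatment may be feasible, and the hypothesis in section 3.4 claims no equivalence between subgroups.
- Section 13.2 targets "no greater than a $\pm 10\%$ SVR difference from the standard 90% SVR". A reader might take 10 points as the plan's margin for every comparison. It is a one-sample target for injectors against an external 90%, and is not stated for HIV status, adherence or OST.

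**Conclusion.** The point holds as a gap in analysis and reporting. Section 13.1 offers tests without an effect measure for HIV status, adherence and OST status, and no measure for the two phase 2 contrasts. The intervals by sub-category do not fill the gap.

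The size is conditional on two-sided 0.05, true SVR12 of 90% v 80% and assumed splits. Within one phase of 100, the difference would be missed about 70% to 90% of the time across 50/50 to 20/80 splits; if 200 are pooled evenly, about 48-56%. A non-significant p-value alone therefore says little about impact. The documents do not show that anyone intends to read it as proof of no effect, so the fault lies in what is left unreported, not in a stated misinterpretation.

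**What to change.** In 13.1, make the SVR12 risk difference with a 95% interval (Newcombe's method, for example) the reported result for each listed comparison (HIV status, adherence, OST status) and for the two phase 2 contrasts (recent IDU or not, collocated OST or not). Keep the chi-squared or Fisher test as secondary. Add a sentence that a non-significant result is not evidence of no effect, and that conclusions rest on the interval. Ten points may be mentioned as an illustrative reference when describing width, but not as a pass/fail margin.

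The cost is wording in the analysis section; no participants, visits or data are added. The downside is that many intervals will be wide: at 50/50 with 90% cured in both groups, the half-width is already ±11.8 points. Many of the comparisons will then have to be called inconclusive.

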1.1 Background Information

Hepatitis C virus (HCV) is a serious infection that chronically infects approximately 135 million people worldwide.(1) There is ongoing acute transmission of HCV, especially in young people who inject drugs,(2) and human immunodeficiency virus (HIV) infected men who have sex with men.(3) Chronic infection with HCV can lead to cirrhosis, liver cancer, and death, and is the leading cause of liver transplantation in the United States.(4) HCV is treatable, and the goal of treatment is to achieve a sustained virologic response (SVR), considered to be a functional cure (absence of plasma HCV RNA 12 weeks after completing therapy). Historically, treatment of HCV using interferon-alfa involved significant toxicities and poor rates of SVR, particularly in patients with HIV and/or black race.

The advent of direct-acting antivirals (DAA) has been revolutionary in the advancement of HCV treatment. DAAs have few side effects, short durations of treatment, and high SVR. In addition, they are effective regardless of race, gender, or HIV status, leaving few barriers to treatment. (5, 6) Therefore, in HCV infected individuals, DAAs have the potential to lower mortality, improve quality of life, reduce long-term costs of complications and interrupt the current global HCV epidemic.(7)

Although DAAs have been extremely effective in curing existing HCV infections, there continues to be transmission of HCV. In 2013, there were an estimated 29,718 cases of acute HCV in the U.S. (8). This acute epidemic of HCV is being driven by individuals with high risk practices, including people who inject drugs (PWID) and men who have sex with men (MSM) (9, 10). Many of these individuals lack access to providers and treatment for HCV (11). Therefore, the current barrier to eradicating HCV is implementing accessible treatment programs in high-risk populations in order to effectively cure those who are chronically infected, in order to prevent transmission of disease.

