5 INTERVENTIONS

5.1 Assessment of Subject Adherence

Adherence will be assessed by subject interview and pill count as per study schedule.

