6.3.1 Adherence monitoring

On weeks 4, 8, 12 participants will meet with study staff to complete counts of remaining pills, as well as answering questions regarding HCV treatment adherence.

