6.3.6 HIV and HCV monitoring

HIV antibody/antigen will be checked at weeks 4, 24, 36, 48, 72, and 96 with a one month window. HCV RNA will be checked per standard of care, and subsequently at weeks 36, 48, 72, and 96 with a one month window.

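### The adherence test in 13.1 uses an SVR12 that counts missing follow-up as failure, so loss to follow-up can look like an effect of adherence on cure

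*Combined protocol and SAP*

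**What the plan says.** Section 13.1 sets the outcome: "The primary outcome is achievement of SVR12 in phase 1 (first 100 enrolled participants"). The analysis includes everyone given at least one dose of a direct-acting antiviral, and "patients without follow-up data are considered to have treatment failure". The next sentence gives the association tests: "Chi-squared or Fisher's exact test will be used to assess the association of SVR12 with baseline characteristics such as HIV-status". It then extends the same tests beyond baseline, naming adherence among the factors: "as well as on treatment factors such as medication adherence and OST status". No other version of SVR12 is defined, and no observed-outcome or sensitivity analysis is named.

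On measuring adherence, section 5.1 says: "Adherence will be assessed by subject interview and pill count as per study schedule". Section 6.3.1 gives the timing: "On weeks 4, 8, 12 participants will meet with study staff to complete counts of remaining pills". Appendix B marks one further adherence check before Week 4. The plan states no adherence cut-off, no rule for a missed count, and no statement on whether participants without counts leave the test.

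The outcome also needs attendance. Section 1.1 describes SVR as "absence of plasma HCV RNA 12 weeks after completing therapy", and section 6.3.6 says: "HCV RNA will be checked per standard of care, and subsequently at weeks 36, 48, 72, and 96 with a one month window".

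**The concern.** Exposure and outcome both depend on turning up. A participant who stops attending has incomplete pill counts or none, and becomes a failure if no follow-up data exist. Depending on how the missing counts are scored, the test may partly compare attendance with attendance.

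Loss need not mean missed doses. Under section 4.4, no study data are collected from a participant who is incarcerated, although staff will try to deliver the remaining drug. Such a person could take every dose, lack a pill count and, if still incarcerated when the SVR12 sample is due, be counted as a failure.

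The précis lists worries about adherence among the reasons insurers restrict treatment in this population. A reported link between adherence and cure would be read in that light, so it should not rest on an unstated scoring rule.

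**Working it through.** The plan gives no figure for this analysis. Its one calculated figure, 85% power in section 13.2, concerns the overall SVR12 proportion and does not enter below.

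**Inputs from the plan:** 100 participants in phase 1; missing follow-up counted as failure; Fisher's exact test. **Assumed, because the documents give no values:** dropout, the proportion adherent, and cure. Cure is set equal in both adherence groups, so the true effect is zero.

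**Step 1. Every lost participant scored non-adherent (the extreme case).** Cure is 95%, and 20% of those retained are non-adherent. With L lost, the retained are 0.8 × (100 − L) adherent and 0.2 × (100 − L) non-adherent. All L join the non-adherent group as failures. Cures are rounded to whole people.

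| Lost | Adherent cured | Non-adherent cured | Fisher p |
|---|---|---|---|
| 5 | 72/76 (95%) | 18/(19+5) = 18/24 (75%) | 0.012 |
| 10 | 68/72 (94%) | 17/(18+10) = 17/28 (61%) | 0.0001 |
| 15 | 65/68 (96%) | 16/(17+15) = 16/32 (50%) | <0.00001 |

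**Step 2. Same people, but the lost keep their last recorded category**, split 80:20 like those retained.

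| Lost | Adherent cured | Non-adherent cured | Fisher p |
|---|---|---|---|
| 5 | 72/80 | 18/20 | 1.0 |
| 10 | 68/80 | 17/20 | 1.0 |
| 15 | 65/80 | 16/20 | 1.0 |

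**Step 3. In between.** Of 10 lost, 5 leave before any count and are scored non-adherent; the other 5 split 4 to 1. The table is 68/76 against 17/24, p = 0.045.

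**Step 4. Last category kept, but dropout linked to adherence.** Now take 70% adherent, cure 90% in both groups, and dropout three times as common in the non-adherent, all after adherence is recorded. With overall dropout d, the adherent lose d/(0.7 + 0.3 × 3) = d/1.6 and the non-adherent lose 3d/1.6.
- d = 10%: losses are 6.25% and 18.75%. Expected SVR12 is 0.9 × 0.9375 = 84.4% against 0.9 × 0.8125 = 73.1%.
- d = 20%: losses are 12.5% and 37.5%. Expected SVR12 is 78.8% against 56.3%.

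In simulation (100 participants, 2,000 runs per setting, Fisher at 0.05), the false-positive rate was 23% at d = 10% and 55% at d = 20%. With half of the dropouts leaving before any count and therefore excluded, it was 11% and 29%. When dropout was unrelated to adherence and adherence came only from attended visits, it was about 2–4%.

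**Step 5. Restricted to participants with observed adherence and an observed RNA result.** The simulated false-positive rate was about 2–4% in every setting. This follows from the set-up, in which dropout is unrelated to cure within each adherence group. It shows that the restriction removes this artefact, not that the restricted estimate is unbiased in practice.

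**The case against.** The strongest reply is that the alarming p-values need a rule the plan never states. A participant who leaves at Week 6 would already have a Week 4 count and could be classified from it. Steps 1 and 2 differ only in that rule, and the result moves from p = 0.0001 to p = 1.0 at 10 lost. This stands. A reader might infer that dropout by itself produces the effect; the documents do not support that. It needs either missed counts scored as non-adherence or dropout linked to adherence.

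A reader might also infer that the test is uninformative however missing counts are handled. That is too strong. If those without counts are excluded and all dropout is early, the simulated false-positive rate is 2–3%.

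Nor does the text make everyone who misses the SVR12 sample a failure. Section 13.1 refers to follow-up data without defining it, and later RNA tests are planned. Carrying the missing-as-failure rule into the association test is itself an inference, although 13.1 offers no other SVR12.

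Finally, restriction has its own bias. Suppose the 10 lost in Step 1 really were non-adherent and really failed. Then 68/72 against 17/28 is the truth, and the restricted 68/72 against 17/18 hides it. This also stands, and it is why the restricted table should accompany the all-treated table and not replace it.

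The stakes are bounded: section 3.1 describes an observational pilot, HCV adherence is an exploratory objective in section 2.3, and 13.1 promises only an association.

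**Conclusion.** The concern holds as a conditional one. Followed as written, 13.1 allows loss to follow-up to appear as an adherence effect on cure, and it does not choose among scoring rules that give opposite answers from the same participants. At 10 lost of 100 with no true effect, p is 0.0001 if all the lost are scored non-adherent, 0.045 if half are, and 1.0 if they keep their last category in proportion to those retained. If the non-adherent drop out three times as often, keeping the last category is not enough: 23% false positives at 10% dropout. These sizes rest on assumed dropout, adherence and cure rates.

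Some lost participants will truly have stopped the drug, so part of an observed association could be real; the planned test cannot separate the two. A reader might take this as a flaw in the main result. It is not: the missing-as-failure SVR12 proportion and its confidence interval are untouched.

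**What to change.** In section 13.1:
- Classify adherence from the pill counts actually obtained, and state that a missed visit is not scored as non-adherence.
- Keep the all-treated adherence table with missing counted as failure. Beside it, report the same comparison among participants with an HCV RNA result at least 12 weeks after the last dose.
- Give the number lost in each adherence category and the number with no count at all.
- State that a conclusion about adherence and virologic cure will be drawn only after reading both tables.
- Leave missing-as-failure in place for the headline SVR12 proportion.

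The cost is a few sentences and one extra table, with no new data collection. The restricted table has fewer participants and may omit true non-adherent failures who never return; showing both tables with the counts of those lost keeps that visible.

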5.2 Concomitant Medications and Procedures

All concomitant prescription and over the counter medications taken during study participation will be recorded. For this protocol, a prescription medication is defined as a medication that can be prescribed only by a properly authorized/licensed clinician.

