6.5 Optional Standard of Care Opioid Substitution Therapy with Buprenorphine

All subjects who meet criteria for opioid use disorder per the DSM-V will be offered initiation of standard of care treatment with buprenorphine for treatment of opioid use disorder. Patients will be seen and monitored as per standard of care. Patients will be offered uptake from day 0 until week 24 of HCV treatment, and will be treated for a 12 month time period, and then transitioned to a community provider. The first day of buprenorphine treatment will be considered day B0. See Appendix A Study Schedule.

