6.7 Early Termination Visit

Participants who discontinue HCV treatment prior to treatment completion for medical or personal reasons will be given the option of being followed as per study schedule for risk assessments, lab monitoring, and ongoing optional PrEP and buprenorphine (if already initiated). Participants who discontinue PrEP or buprenorphine will continue to be monitored per the HCV study schedule, however will no longer have monitoring specific to PrEP or buprenorphine. The participant should have an end of treatment visit scheduled as soon as possible after all therapy is discontinued. The reason for any early termination will be documented.

7 Potential Risks and Benefits

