APPENDIX B: Study Schedule

					M1	M2	M3	M6	M9	M12	M18	M24
HCV Treatment	Screening	Day 0	Week 2	Week 3	Week 4	Week 8	Week 12	Week 24	Week 36	Week 48	Week 72	Week 96
MD Visit	X	X*			X*	X*	X*	X*				
HCV SOC Labwork	X				X		X	X				
HCV RNA	X				X		X	X		X	X	X
HCV Adherence			X		X	X	X					
Stored Samples	X				X		X	X		X		X
Fibroscan	X							X		X		X
PrEP Retrospective Questionnaire										X	X	X
PrEP**		Day P0			Week P4		Week P12	Week P24	Week P36	Week P48		
MD Visit		X			X		X	X	X	X		
Adherence					X		X	X	X	X		
Labwork		X			X		X	X	X	X		
Buprenorphine***		Day B0	Week B2		Week B4	Week B8	Week B12	Week B24	Week B36	Week B48		
MD Visit		X	X		X	X	X	X	X	X		
Urine Buprenorphine			X		X	X	X	X	X	X		
Assess Retention			X		X	X	X	X	X	X		
Risk Monitoring	Screening	Day 0	Week 2	Week 3	Week 4	Week 8	Week 12	Week 24	Week 36	Week 48	Week 72	Week 96
Epidemiologic Survey	X											
HCV PRO	X						X	X				
HIV Risk/SEP Assessment		X			X		X	X		X	X	X

Urine Drug Screen	X				X		X	X		X	X	X
HIV 4 th gen	X				X		X	X		X	X	X
AUDIT-C	X							X		X		X
ACE								X				
GMA Assessment****												
GMA Training and Cell Distribution		X										
Adherence Packet -4		X										
Adherence Packet-2					X		X	X		X		
Return Cell Phone										X		

*Study participants will be offered PrEP and buprenorphine at every MD visit if have not currently uptaking

**PrEP uptake is optional. Day P0 can be on any day from Day 0 to Week 24 of HCV treatment.

***Buprenorphine uptake is optional. Day B0 can be on any day from Day 0 to Week 24 of HCV treatment.

****GMA participation is optional.

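### Section 13.1 does not say when OST status is taken; if it is taken after Day 0 and missing SVR12 counts as failure, the Objective 7 comparison can be biased in favour of OST

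*Combined protocol and SAP*

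**What the plan says.** Section 13.1 plans chi-squared or Fisher's exact tests of SVR12 against two kinds of factor: baseline characteristics, with HIV status as the example, and "on treatment factors such as medication adherence and OST status". It gives no date, window or minimum exposure for OST status, and no landmark, time-varying or adjusted method. This is the only analysis in 13.1 that addresses Secondary Objective 7 (section 2.2), the impact of OST on HCV treatment outcomes.

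For the intention-to-treat analysis, the same section includes everyone with at least one DAA dose and adds that "patients without follow-up data are considered to have treatment failure".

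On buprenorphine, section 6.5 says "Patients will be offered uptake from day 0 until week 24 of HCV treatment", and a footnote to Appendix B says "Day B0 can be on any day from Day 0 to Week 24 of HCV treatment". Another footnote has it re-offered at each physician visit to those not taking it; the schedule shows these at Day 0 and Weeks 4, 8, 12 and 24. Section 1.1 places SVR 12 weeks after the end of therapy. The length of the DAA course is not stated, but section 6.3.1 schedules adherence checks to Week 12 ("On weeks 4, 8, 12 participants will meet with study staff to complete counts of remaining pills"). For a 12-week course, SVR12 therefore falls at about Week 24.

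For participants who stop DAAs early, section 6.7 offers continued follow-up with "ongoing optional PrEP and buprenorphine (if already initiated").

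**The concern.** OST status can change during follow-up, and a participant has to be attending to move from no OST to OST. Someone who leaves at Week 6 without having started can no longer be classed as exposed. If that person also counts as a treatment failure for want of an SVR12 result, the no-OST group collects failures that have nothing to do with OST. This is immortal-time bias, and here it favours OST.

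The label in 13.1 points towards a status read after baseline, and the start window can run up to the outcome visit. With status undefined, an analyst could also choose among Day 0, ever by Week 12 and on OST at a given visit after seeing the data, and these can give different answers. Part of an apparent OST benefit in Objective 7 could then reflect only who stayed long enough to start.

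**Working it through.** **The plan's own figure.** The only power statement (13.2) is 85% for the single-arm primary test: null 90%, alternative 80%, n = 100. It reproduces: (0.10 × √100 − 1.96 × √(0.9 × 0.1)) / √(0.8 × 0.2) = (1 − 0.588)/0.4 = 1.03, and Φ(1.03) = 84.9%. It does not bear on OST, for which no power or effect size is given.

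**Inputs.** From the documents: offers at Day 0 and Weeks 4, 8, 12 and 24; missing = failure; n = 100 (Phase 1); Fisher test, taken at two-sided 0.05. Assumed, because the documents are silent: 95% cure if retained; cumulative dropout d of 10%, 20% or 30% by Week 24 at a constant hazard; 0% or 30% on OST at entry; OST has no effect on cure or retention. Uptake takes one of two patterns:
- equal: 10%, 20% or 30% at each offer, paired with d;
- mostly at Day 0: for d = 20%, for instance, 45%, 15%, 8%, 5% and 2% at the five offers.

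**One scenario by hand** (d = 20%, nobody on OST at entry, 20% uptake per offer, starts through Week 12 counted). The share still in follow-up at week t is 0.8^(t/24): 0.963 at Week 4, 0.928 at Week 8, 0.894 at Week 12 and 0.800 at Week 24.

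- Ever on OST: 0.2 + 0.16 × 0.963 + 0.128 × 0.928 + 0.1024 × 0.894 = 0.565. Not on OST: 0.435.
- Retained to Week 24: on OST 0.8 × (1 − 0.8⁴) = 0.472; not on OST 0.8 × 0.8⁴ = 0.328.
- SVR12: on OST 0.95 × 0.472/0.565 = 79.5%; not on OST 0.95 × 0.328/0.435 = 71.5%. The spurious difference is 8.0 points.

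With Day 0 status, retention is 0.8 in both groups, so SVR12 is 0.95 × 0.8 = 76% in each. With a Week 4 landmark among those still followed, it is 0.95 × 0.8/0.963 = 78.9% in each. The difference is zero either way.

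**All scenarios** (10,000 simulated trials each, no true effect; ranges over dropout and OST at entry):

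| How status is taken | Uptake | Difference favouring OST | False rejection |
|---|---|---|---|
| Ever by Week 12 | mostly Day 0 | 1 to 3 points | 3% to 5% |
| Ever by Week 12 | equal per visit | 2 to 15 points | 4% to 25% |
| Ever by Week 12, half of missing results recovered | equal per visit | 1 to 8 points | 3% to 11% |
| Day 0 | either | within 0.1 point | 2% to 4% |
| Week 4 landmark | either | within 0.3 point | 2% to 4% |

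The third row allows for participants who return later, since HCV RNA is also measured "subsequently at weeks 36, 48, 72, and 96 with a one month window".

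**Dependence on missing = failure.** If the association tests used only participants with an SVR12 result, cure would be 95% in both groups under these assumptions and the dropout artefact would vanish.

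**Section 6.7.** If it barred new starts after early DAA cessation, a second route would exist without dropout. Assuming 5% or 10% stop early with 50% SVR, it adds 2 or 4 points with equal uptake (20% per offer) and about 1 point with uptake mostly at Day 0. A landmark requiring only follow-up leaves 0.5 or 0.9 point; also requiring participants to be on DAAs removes it.

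**The case against.** The strongest reply is that 13.1 never says status means ever started after Day 0. Read as Day 0 status, the artefact is absent. This stands: what is established is an undefined variable that can produce bias. The on-treatment label does, however, point away from the Day 0 reading.

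Second, missing = failure is stated for the intention-to-treat analysis, and carrying it to the association tests is an inference. That also stands as a condition, although the paragraph names no other rule.

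Third, scale. The upper figure of 15 points needs 30% dropout together with 30% uptake at every visit; with 30% dropout and 10% uptake it is 8 points. Phase 1 enrols people who injected opioids within three months and the offer opens on Day 0, so uptake mostly at Day 0 is at least as credible, and the effect is then small. Participants already on OST at entry are not subject to the mechanism at all.

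Three stronger readings are tempting, and the documents do not support them:
- A reader might count starts through Week 24, which gives up to 25 points with equal uptake. A start at the SVR12 visit is hard to call an on-treatment factor when adherence checks end at Week 12.
- A reader might infer that 6.7 forbids starting buprenorphine after DAAs stop. It says what may continue; it does not bar a start, and 6.5 offers buprenorphine until Week 24 without excepting those who have stopped.
- A reader might extend the bias to the collocated versus non-collocated OST comparison. Both groups there are on OST, and someone who leaves before starting belongs to neither, so the mechanism does not carry over. Only the missing time point is shared.

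Finally, this is a non-randomised pilot and 13.1 speaks of association. But Objective 7 asks for impact, so a comparison free of this artefact is worth having.

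**Conclusion.** The point holds conditionally. If OST status is taken after Day 0 and missing outcomes count as failures in this test, the planned comparison can favour OST when OST does nothing. The true size cannot be determined, because dropout, uptake and OST at entry are not given; the Week 12 rows of the table are a range under stated assumptions, running from negligible to material. Section 6.7 may add a little under one reading of it.

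A reader might go further and conclude that the Objective 7 result will be biased towards OST overall. That does not follow: who chooses OST is a separate source of confounding that could act in either direction, so the net bias is unknown. The Phase 1 primary SVR12 proportion does not use OST status and is unaffected. The plan should be changed on this point because the remedy is cheap and removes the artefact under every assumption tried.

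**What to change.** In 13.1, for Objective 7:
- Classify OST status (any agent, any source) at Day 0 in all treated participants.
- Add a Week 4 landmark analysis: status at Week 4 among those still in follow-up and on DAAs at Week 4, comparing SVR12 from there.
- In both, do not count later starts as exposed. Either analysis may be named as the main one.
- State that missing = failure applies to the association tests, or name the rule that does.
- For collocated versus non-collocated OST, state the same time point; nothing more is needed there.

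Sections 6.5 and Appendix B can stay as they are. No new visits or data are required: the first day of buprenorphine is identified as Day B0 under 6.5, and for other OST section 5.2 provides that "All concomitant prescription and over the counter medications taken during study participation will be recorded".

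The cost is some loss of sensitivity. Later starters are classed as unexposed, which dilutes any true effect; in the scenarios above, about 3 to 22 of 100 start after Week 4 and by Week 12, and Day 0 status also leaves out those who start at Week 4. The landmark drops those lost before Week 4 (about 2 to 6 of 100 in these scenarios) and any who stopped DAAs by then. Day 0 status keeps every treated participant. Neither analysis deals with confounding by who takes up OST, and the report should say so.
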